Multiple-Cycle Extension: In Studies 1, 2, and 3, patients had the option of continuing into a multiple-cycle extension for up to 5 additional cycles of chemotherapy receiving the same treatment as assigned in cycle 1. At day 6 to 8 following initiation of chemotherapy, patients were asked to recall whether they had any episode of vomiting or retching or nausea that interfered with normal daily life. The results are summarized by study and treatment group in the figure below.

■ Control ■ Rolapitant

[figure not shown]

Figure 1: No Emesis and No Nausea Interfering with Daily Life over Cycles 2-6

7.3 Study Purpose/Rationale

The purpose of this randomized study is to primarily assess efficacy, in addition to patient preference, patient satisfaction and patient compliance of rolapitant plus ondansetron vs. ondansetron monotherapy for the prevention of chemo-radiation-induced nausea and vomiting (chemo-RINV) in malignant glioma patients receiving standard RT and concomitant TMZ (Stupp regimen).

We conducted the first phase 2 single arm trial of palonosetron (PAL), a long acting 5-hydroxytryptamine (5-HT $_3$) receptor antagonist (5HT $_3$ -RA), for the prevention of RINV in primary MG subjects receiving RT (54-60 Gy) and concomitant multi-dose, daily TMZ (75 mg/m 2) +/- bevacizumab. Results from this study demonstrate that a 5HT $_3$ -RA, such as PAL or ondansetron, can be safe and effective, however based on the results, there is still room for improvement of anti-emetic response related to CR rates and HRQoL, which could be addressed by combining a 5-HT $_3$ -RA and NK $_1$ -RA 12 . PAL was safe and effective; however, there is room for improvement in the CR rates and HRQoL, which may be achieved with rolapitant plus ondansetron, a potentially more effective combination anti-emetic regimen. Additionally, PAL is only available as an IV injection in the United States whereas ondansetron can be administered orally, making it a more patient-friendly drug. The most studied agents in the RINV settings are the 5HT $_3$ -RAs, with overall moderate response and low toxicity. However, agents such as the tachykinin NK-1 receptor antagonist may play a role in improving response rates, but there needs to be further studies in randomized controlled trials. ¹³

The oral combination of rolapitant plus ondansetron has not been studied in the prevention of RINV using multi-dose chemotherapy especially in individuals with malignant glioma. Additional advantages to using rolapitant plus ondansetron in the setting of radiation with concurrent multi-dose oral chemotherapy are that it avoids side effects associated with intravenous administration (e.g. palonosetron) and eliminates treatment room costs. Furthermore, rolapitant, as opposed to the aprepitant or netupitant, is not a CYP3A4 inhibitor or inducer of for common drugs used in glioma patients (e.g. dexamethasone, enzyme-inducing anticonvulsants, or irinotecan) thus reducing drug-induced side effects. The NK₁ antagonist EMEND® (aprepitant) was approved by the US Food and Drug Administration and by the European Medicines Agency for the prevention of acute and delayed CINV associated with highly emetic chemotherapy (HEC- i.e. high dose cisplatin) and MEC when used in combination with a 5-HT₃ antagonist and a corticosteroid. Dosage adjustment of concomitantly administered drugs is necessary with aprepitant, which is a mixed inducer/inhibitor of cytochrome P450 (CYP) 3A4 and also affects other CYP enzymes. Rolapitant has been free of clinically relevant drug interactions in studies conducted to date, has rapid and good brain penetration which may contribute to its quick onset of action, and a long half-life that allows for dosing only once during each cycle of chemotherapy. Rolapitant has been selected as a promising agent to address this and other shortcomings of existing therapy. As described above, PET occupancy studies as well as clinical efficacy data support the use of only a single dose of rolapitant to protect patients from CINV. Efficacy or complete response be assessed during weeks 1-2. Complete response (CR) is defined as the proportion of patients without an emetic episode or use of rescue medication while receiving radiation and concomitant temozolomide).

Patient-centered care as it relates to patient preference and satisfaction has become one of the major goals in healthcare reform and transformation. Patient centeredness is a dimension of health care quality because of its connection with desired aims, like safety and effectiveness. Patient centeredness and satisfaction shifts the control from the hands of those who give care into the hands of those who receive it. Patient satisfaction with healthcare medications has been shown to affect treatment-related behaviors such has their likelihood of complying and continuing to use their medication correctly. ¹⁶Thus, patient satisfaction translates into improved patient-centered outcomes and quality of care. The basis for this assessment will be overall patient medication satisfaction/preference at the end of week 3 and 6. More descriptive data (effectiveness, convenience and global satisfaction) relating to a patient's choice will be measured as a secondary outcome by the reliable and validated TSQM-9 tool.

Standard practice within the PRTBTC for prophylactically preventing nausea and vomiting associated with chemoradiation is the administration of ondansetron. With the administration of ondansetron orally 1-3

times a day for multiple days, compliance is a problem within this patient population. Newer approaches to treatment such as a single dose rolapitant should have fewer or minimal compliance problems. Hence, there is interest in understanding patient efficacy and preference relative to ondansetron. Compliance of ondansetron vs. rolapitant and ondansetron is also of interest.

Evidenced-based guidelines and clinical research recommend that future studies should consider the use of 5HT₃-RAs and NK1=RA with current therapies and in other clinical settings, such as radiation therapy. Studies at the PRTBTC at Duke have evaluated intravenous palonosetron in RINV. However, rolapitant has not been studied in the prevention of RINV in malignant glioma. Rolapitant plus ondansetron in the setting of radiation with concurrent oral chemotherapy (e.g. temozolomide) is advantageous in avoiding intravenous administration side effects and treatment room costs. Furthermore, rolapitant and ondansetron as opposed to ondansetron monotherapy (up to three times a day for seven day/week) may ultimately increase compliance and decrease costs. The single dose rolapitant in combination with ondansetron may be beneficial to the brain tumor patient population for three specific reasons: (1) rolapitant may increase antiemetic efficacy and (2) compliance in patients with gliomas who often "forget" to take multiple oral dosed medications due to memory impairment (3) and may prevent toxicity (e.g. interaction with enzyme inducing anticonvulsants) that is associated with administration of other longer acting antiemetics (e.g. aprepitant). **Ultimately, rolapitant plus ondansetron may improve overall efficacy (CR rates), cost, HRQoL and patient satisfaction.**

8 OBJECTIVES AND ENDPOINTS

| | Objective | Endpoint | Analysis |
|------------------|--|--|--------------------|
| Primary | Compare the efficacy of rolapitant plus ondansetron vs. ondansetron monotherapy in the prevention of nausea and vomiting, as measured by the overall complete response (CR) rate, among malignant glioma patients during RT and concomitant TMZ | Complete response (CR) rate associated with rolapitant plus ondansetron and ondansetron alone during the first two weeks of RT and concomitant TMZ. The CR rate is defined as the proportion of patients with no emetic episode or use of rescue medication while receiving radiation and concomitant TMZ. The CR rate will be assessed via the modified MASCC Antiemesis Tool (MAT) within daily diary. ¹⁷ | See section 15.4 |
| KEY Secondary | Assess whether malignant glioma patients receiving RT and concomitant TMZ are more satisfied with rolapitant plus ondansetron vs. ondansetron monotherapy for the prevention of RINV | The percentage of patients who prefer rolapitant plus ondansetron over ondansetron alone, as determined by response to the question with "Which nausea medication regimen was I most satisfied with?" | See section 15.5.1 |
| Secondary | Describe the rationale behind a patient's satisfaction with antiemetic preference based upon effectiveness, convenience & global satisfaction | Mean patient satisfaction scores during weeks 3 and 6 for effectiveness, convenience, and global satisfaction for ondansetron pill and rolapitant plus ondansetron using the 9-item TSQM-9 patient satisfaction survey. ¹⁶ Three subscales are computed: effectiveness (3 items), convenience (3 items), and global satisfaction (3 items). | See section 15.5.2 |
| Secondary | Compare the efficacy of rolapitant plus ondansetron vs. ondansetron monotherapy in the prevention of nausea and vomiting separately, as measured by the respective CIN, CIV -CR rates, among malignant glioma patients during RT and concomitant TMZ | The CR outcomes for nausea will be defined in comparable terms (no use of rescue medication for nausea). The CR outcome for vomiting will be defined in comparable terms (no use of rescue medication for vomiting). The CIN, CIV CR rate will be assessed via the modified MASCC Antiemesis Tool (MAT) within daily diary. | See section 15.5.2 |
| Secondary | Evaluate patient compliance with rolapitant plus ondansetron and ondansetron monotherapy | The compliance rate defined as the percentage of days that rolapitant plus ondansetron or ondansetron alone were used during the six weeks | See section 15.5.2 |
| Secondary | Assess the safety of rolapitant plus ondansetron in the prevention of RINV in primary glioma patients receiving RT and concomitant TMZ | The percentage of patients experiencing a grade ≥3 treatment-related toxicity. Toxicity (adverse events) will be assessed throughout the 6-week treatment period. This data will be collected via NCI Common Toxicity Criteria (CTC) (vs 4) | See section 15.5.2 |

9 INVESTIGATIONAL PLAN

9.1 Study Design

This proposed single center study is a randomized phase II trial of rolapitant plus ondansetron vs. ondansetron monotherapy for the prevention of RINV in primary malignant glioma subjects receiving radiation therapy (RT) and concomitant multi-dose temozolomide (TMZ). All eligible subjects should receive a planned total dose of 54-60 Gy of radiation and 75 mg/m² of temozolomide daily for a total of six weeks. Glioma patients will be randomized in an unblinded fashion to receive one of two treatment sequences of antiemetic therapy for the prevention of nausea and vomiting associated with RT and concomitant TMZ.

Sequence A involves administration of ondansetron alone for 3 weeks followed by the use of rolapitant X 1 dose plus daily ondansetron for 3 weeks; whereas, sequence B involves the use of rolapitant X 1 dose plus daily ondansetron for 3 weeks followed by 3 weeks of daily ondansetron alone. For the rolapitant plus ondansetron weeks (1 or 4), patients will self-administer the oral rolapitant pills (180 mg dose) X 1 dose, 1-2 hours before the planned week of radiation fraction (see schema). Subjects will be given a prescription for ondansetron 8 mg pills to be taken 30 minutes before their TMZ dose. After the start of radiation therapy, the type of additional rescue antiemetic medication, if needed will be left up to the investigator's discretion, with what is in the best interest of the subject. Subjects will be educated that they are allowed to take rescue antiemetic medication in either arm. If the subject experiences nausea and vomiting and does take a rescue antiemetic, the subject will be asked to record the use of additional antiemetic in a medication log provided to them. Subjects will complete weekly medication logs and surveys (see appendices) to capture study outcomes. Subjects will be told that the study is voluntary and that they may exit at any time if they wish.

Approximately 170 patients will provide informed consent in order that 160 patients be randomized to either treatment sequence A or B. The 170 estimate is to allow for screen failures and dropout rates. All subjects must give written informed consent to participate in the study. Patients will be screened -28 - 0 days prior to the start of the study. During this time period the following information will be recorded: physical examination; vital signs and weight; laboratory studies (complete blood count with differential, blood chemistries, liver function tests and urinalysis): medical history; concomitant medications (steroids and anticonvulsants) and predictors of RINV (irradiation site, planned dose treatment field, alcohol intake, gender, age etc.). Laboratory evaluations, performance status, concomitant medications, and adverse events for final eligibility should be confirmed within 2 weeks of initiating radiation with concomitant TMZ. Patients will obtain standard of care blood work (per local oncologist) (complete blood count with differential, blood chemistries, liver function tests). Toxicity will be assessed based on the Common Toxicity Criterion (CTC version 4). The patient will be asked to complete the MASCC Antiemesis Tool (MAT- see appendices) nausea and vomiting questionnaire on day 0 (baseline) and days 1, 2, 4, and 7 of each week of radiation therapy. In addition, they will be asked to record their use of any antiemetic rescue medication.

At the end of weeks 3 & 6, the subject will be asked to fill out a Treatment Satisfaction Questionnaire for Medication (TSQM-9- see appendices) and will be asked at the end of week 6 to choose which antiemetic they prefer.

9.2 Standard of Care Chemotherapy Treatment Plan

Temozolomide is an oral alkylating agent which has demonstrated anti-tumor activity as a single agent in the treatment of recurrent glioma. As stated previously, Stupp et al (2005) have demonstrated an increase in efficacy of temozolomide in combination with radiation therapy in the adjuvant treatment of primary malignant gliomas. In addition, the regimen was considered safe. Non-hematological grade 2 toxicities included: Fatigue (26%), other constitutional symptoms (7%), rash and dermatologic side effects (9%), infection (1%), vision (14%), and nausea and vomiting (13%). Grade 3 / 4 non-hematological toxicities occurred <10%: Fatigue (7%), other constitutional symptoms (2%), rash and dermatologic side effects (1%), infection (3%), vision (1%), and nausea and vomiting with a 5HT₃-RA (<1%). Thus, this safe and standard regimen will be utilized in this protocol. Daily temozolomide therapy will be calculated at a dose of 75 mg per square meter of

body surface area per day and be administered 7 days a week from the first until the last day of radiation therapy or a total of 42 days. Additional clinical and laboratory assessments will be at the discretion of the radiation therapist and oncologist.

9.3 Standard of Care Radiation Treatment Plan

As dictated by the Stupp (2005) regimen, radiation therapy will be administered as fractionated focal irradiation in daily fractions of 1.8-2 Gy given 5 days a week for \sim 6 weeks for a total of 54-60 Gy. Patients will be followed closely by a local radiation therapist throughout treatment. The radiation therapist and oncologist will conduct the standard physical exams and obtain the lab work necessary for the eligibility. Additional clinical and laboratory assessments will be at the discretion of the radiation therapist and oncologist.

9.3.1 Dose Definition and Schedule

The external beam radiation therapy (XRT) plan will be determined at the discretion of the local radiation therapist dependent on tumor size and location. It should begin 2-6 weeks after surgery. One treatment of 1.8-2.0 Gy will be given daily, 5 days per week, (30-33 fractions over less than seven weeks) for a total of 54-60 Gy. All portals shall be treated during each treatment session. Doses are prescribed at the maximum dose line encompassing \geq 95% of the target volume.

9.3.2 Physical Factors

Treatment shall be delivered on megavoltage machines of energy ranging from 4 to 18 MV photons. Selection of the appropriate photon energy should be based on optimizing the RT dose distribution within the target volume and minimizing dose to non-target normal tissue. Photon energies > 10 MV should be utilized only in dual energy beam arrangements using at least one beam with energy < 10 MV. Source skin distance for SSD techniques or source axis distance for SAD techniques must be at least 80 cm.

9.3.3 Localization, Simulation, and Immobilization

The patient shall be treated in the supine or another appropriate position for the location of the lesion. A head-holding device that is transparent to x-rays and provides adequate immobilization must be utilized at all times during planning and therapy to ensure reproducibility.

The initial target volume shall include the contrast-enhancing lesion and surrounding edema (if it exists) demonstrated on the pre-operative MRI plus a 2.0-cm margin. If no surrounding edema is present, the initial target volume should include the contrast-enhancing lesion plus a 2.5-cm margin. This primary target volume will be treated to 45-46 Gy in 23-25 daily fractions, at 1.8-2.0 Gy per fraction.

The boost volume will be based on the post-operative MRI performed during treatment planning. After 45-46 Gy, the boost volume will include the contrast-enhancing lesion plus a 1.5-cm margin or, if minimal contrast-enhancing lesion is present at a portion of the resection cavity on MRI, the surgical defect plus a 2.0-cm margin, whichever is greater at that segment of the MRI image. The boost volume will be treated to an additional 14-14.4 Gy in 7-8 daily fractions, 1.8-2.0 Gy per fraction. This will bring the total target dose to 54-60 Gy in 30-33 fractions. All parts of the target volumes are to receive at least 100% but no more than 110% of the dose at the prescription isodose line.

9.3.4 Treatment Planning and Safety

Treatment plans may include opposed lateral fields, a wedge pair of fields, rotation, or multiple-field techniques, including intensity-modulated radiotherapy (IMRT) and volumetric-modulated arc therapy (VMAT). MRI-guided 3D treatment planning is necessary to assure accuracy in the selection of field arrangements. Isodose distributions for the primary and boost target volume are required on all patients, including those treated with parallel-opposed fields. A composite plan is required showing the respective target volumes. The inhomogeneity across the target volume shall be kept to a minimum.

The maximum dose should be no higher than 112% of the prescription. Possible side effects include swelling of the brain, hair loss, localized skin irritation, low blood counts, fatigue, memory loss, hearing loss, nausea and/or vomiting, loss of appetite, headaches, radiation necrosis (death of tissue or skin), and secondary cancer.

9.3.5 Dose Limitations to Critical Structures

The lens and cervical spine must be shielded from the direct beam at all times. The maximum dose to the optic apparatus (optic chiasm, optic nerves, and eyes) must be limited to 54 Gy, and the brain stem limited to 60 Gy.

9.3.6 Safety Considerations

Safety will be assessed throughout the six weeks of radiation and 2 weeks post radiation using adverse event reporting by the clinical research nurse (CRN) using the Common Toxicity Criterion (CTC version 4.0). Monthly meetings conducted to review all adverse events and safety events with the PI, CRN, and CRC is standard of practice within the PRTBTC.

9.4 Anti-emetic Treatment

9.4.1 Antiemetic Treatment Plan

Sequence A involves administration of ondansetron alone for 3 weeks followed by the use of 1 dose of rolapitant plus daily doses of ondansetron for 3 weeks. Sequence B involves the use of 1 dose of rolapitant plus daily doses of ondansetron for 3 weeks followed by 3 weeks of ondansetron alone. For the rolapitant plus ondansetron weeks (1 or 4), patients will self-administer the single oral dose of rolapitant 1-2 hours before the first fraction of radiation on the planned week. Subjects will be given a prescription for ondansetron 8 mg pills to be taken 30 minutes before their daily TMZ dose. After the start of radiation therapy, the type of additional rescue antiemetic medication, if needed will be left up to the investigator's discretion. Subjects will be informed that they are allowed to take rescue antiemetic medication in either arm of the study. If the subject experiences nausea and vomiting and does take a rescue antiemetic, the subject will be asked to record the use of an additional antiemetic in the medication log provided to them. Subjects will complete weekly medication logs and surveys (see appendices) to capture study outcomes. Subjects will be told that the study is voluntary and that they may exit at any time if they wish.

9.4.2 Missed Doses

Patients will be reminded by the study team via a weekly phone call to take daily ondansetron and the rolapitant prior to weeks 1 or 4 of radiation depending on the assigned sequence (A vs. B). The time and date of ondansetron and rolapitant administration will be recorded in the patient medication log (see appendices). Subjects will be required to contact their treating physician for instructions if they forget to take rolapitant before the scheduled week of radiation or ondansetron before their daily chemotherapy. Rescue medication (e.g. ondansetron 8 mg p.o.) will be used to make up a missed dose.

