5 PROTOCOL SYNOPSIS AND RESEARCH SUMMARY

5.1 Purpose

The purpose of this two-arm randomized phase 2 study is to assess the efficacy and patient satisfaction of oral rolapitant plus ondansetron vs. oral ondansetron *monotherapy* in malignant glioma (MG) patients receiving six weeks of standard cranial radiation therapy (RT) and concomitant temozolomide (TMZ).

Primary Objective:

Compare the efficacy of rolapitant plus ondansetron vs. ondansetron mono therapy in the prevention
of chemoradiation-induced nausea and vomiting (chemo-RINV), as measured by the overall complete
response (CR) rate (where CR is defined as no emesis, no rescue antiemetic), among malignant glioma
patients during the standard ~ 6 weeks of RT and concomitant multi-dose TMZ

Secondary Objectives:

- KEY secondary objective: Assess whether malignant glioma patients receiving RT and concomitant TMZ
 are more satisfied with rolapitant plus ondansetron vs. ondansetron monotherapy for the prevention of
 chemo-RINV
- 2. Describe the rationale behind a patient's satisfaction with antiemetic preference based upon effectiveness, convenience and global satisfaction
- 3. Compare the efficacy of rolapitant plus ondansetron vs. ondansetron monotherapy in the prevention of nausea and vomiting separately, as measured by the respective CIN, CIV -CR rates, among malignant glioma patients during RT and concomitant TMZ
- 4. Evaluate compliance of rolapitant plus ondansetron vs. ondansetron monotherapy
- 5. Assess the safety of rolapitant plus ondansetron vs. ondansetron monotherapy in the prevention of RINV in glioma patients receiving RT and concomitant TMZ

Hypotheses

1. This is a hypothesis-testing protocol. Hypothesis: rolapitant plus ondansetron will produce an equally or a more effective RINV CR rate when compared to ondansetron monotherapy in glioma patients receiving RT and concomitant TMZ.

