9.4.3 Concomitant Medications

Prophylactic medication for the prevention of nausea and vomiting 24 hours prior to the start of radiation therapy through the full course of radiation therapy is prohibited, with the exception of the study drugs. Corticosteroids will be allowed for treatment of cerebral swelling. Rescue medication for treatment of nausea and vomiting is permitted while receiving radiation therapy at the discretion of the investigator. The date(s) of the rescue medication administration will be recorded in the patient medication log (see appendices).

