15.4.1 Variable

Complete response (CR) rate associated with rolapitant plus ondansetron and that associated with ondansetron during the first two weeks of RT and concomitant TMZ is defined as the proportion of patients with no emetic episode or use of rescue medication while receiving radiation and concomitant TMZ. The CR rate will be assessed via the modified MASCC Antiemesis Tool (MAT).¹⁷

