15.5.2 Other Secondary Objectives

Mean patient satisfaction scores for effectiveness, convenience and global satisfaction, will be computed based upon responses to the TSQM-9 treatment satisfaction survey¹⁶ that patients complete at the end of week 3 after treatment with ondansetron alone or combination treatment. Three subscales will be computed: effectiveness (3 items), convenience (3 items), and global satisfaction (3 items). Assuming there is no evidence of a carry-over effect, a paired t-test will be conducted comparing satisfaction with combination treatment and with ondansetron treatment alone.

The efficacy of rolapitant plus ondansetron vs. ondansetron monotherapy in the prevention of nausea and vomiting will be separately assessed, as measured by the respective CIN, CIV CR rates, among malignant glioma patients during RT and concomitant TMZ. The CR outcome for nausea will be defined as no use of rescue medication for nausea, while the CR outcome for vomiting will be defined as no use of rescue medication for vomiting. The CIN and CIV CR rates will be assessed via the modified MASCC Antiemesis Tool (MAT).

For each 3-week treatment regimen, compliance is defined as the percentage of days that pills were appropriately used. The distribution of compliance during treatment with ondansetron alone and with combination treatment will be described with a frequency distribution. A nonparametric paired test (e.g. Wilcoxon) may be used to compare compliance within the two regimens (as documented on the medication logs).

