15.7 Sample Size Calculation

15.7.1 Original Study Design

One hundred seventy (170) glioma patients will be enrolled with the expectation that 160 patients will be randomized to receive one of two treatment sequences of anti-emetic therapy for the prevention of nausea and vomiting associated with RT and concomitant TMZ. A permutated block randomization with an allocation ratio of 1:1 will be used to assign patients to sequence A or B. Sequence A involves a 3-week regimen of daily ondansetron followed by a 3-week regimen consisting of rolapitant (day 22 only) and daily ondansetron; whereas Sequence B involves a 3-week regimen of rolapitant (day 1 only) and daily ondansetron followed by a 3-week regimen of daily ondansetron. The study has one primary and one KEY secondary endpoint: CR rate and patient overall preference for ondansetron treatment with or without rolapitant. Though the primary CR rate endpoint will focus on treatment during the first 2 weeks of RT and TMZ, a crossover design is proposed so that a patient will experience both modes of treatment, and be equipped to make a comparative assessment of preference.

Power Calculations for Complete Response, Primary Endpoint: The power of the comparison of ondansetron and the combination of ondansetron and rolapitant relative to the CR rate during the initial 2 weeks of treatment with RT and TMZ will be considered here. This comparison will focus on the anti-emetic experience during the first regimen of the two treatment regimens that the patient will receive. Let

p₁ = overall complete response rate for the first 2 weeks of treatment with the combination antiemetic regimen, and

 p_0 = overall complete response rate during the first 2 weeks of treatment with ondansetron alone.

The hypothesis that will be assessed is whether the CR rate with combination treatment is greater than that with ondansetron alone. Specifically, the hypothesis that will be tested is as follows:

 H_0 : $p_1 \le p_0$ versus H1: $p_1 > p_0$

Temozolomide prescribing information reports a vomiting rate of 20% with concomitant RT + TMZ. Anti-emetic treatment failure includes the occurrence of vomiting or the use of an anti-emetic for nausea and/or vomiting. Therefore, we anticipate that approximately 25% of patients receiving ondansetron alone to either vomit or receive an anti-emetic. Equivalently, a CR rate of 75% is anticipated with ondansetron alone.

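### Section 9.4.2 labels a replacement for a missed dose as rescue, so read literally a symptom-free patient fails CR; probably a labelling slip, which 15.4.1 should settle

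*Combined protocol and SAP*

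**What the plan says.** Section 9.4.2 covers a forgotten rolapitant dose and a forgotten daily ondansetron dose. The patient is to contact the treating physician, and then: "Rescue medication (e.g. ondansetron 8 mg p.o.) will be used to make up a missed dose". No symptom is required.

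CR is defined three times, each time without limiting rescue by reason:

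- 5.1: "CR is defined as no emesis, no rescue antiemetic"
- 8: "The CR rate is defined as the proportion of patients with no emetic episode or use of rescue medication"
- 15.4.1: "the proportion of patients with no emetic episode or use of rescue medication while receiving radiation and concomitant TMZ"

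The primary comparison uses CR over the first two weeks (15.4.1, 15.4.2).

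Other sections link rescue to symptoms:

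- 9.4.1: "If the subject experiences nausea and vomiting and does take a rescue antiemetic, the subject will be asked to record the use"
- 9.4.3: "Rescue medication for treatment of nausea and vomiting is permitted while receiving radiation therapy at the discretion of the investigator"
- 15.5.2: "The CR outcome for nausea will be defined as no use of rescue medication for nausea", with parallel wording for vomiting
- 15.7.1, behind the planned 75% control rate: "Anti-emetic treatment failure includes the occurrence of vomiting or the use of an anti-emetic for nausea and/or vomiting"

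Compliance is a separate secondary endpoint (8, 15.5.2). Section 7.3 describes compliance with oral ondansetron as a problem in these patients but gives no rate.

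**The concern.** The label in 9.4.2 and the unqualified CR definition together produce a result that the endpoint is not meant to give. A patient who never felt sick, forgot a tablet and took it later would count as an antiemetic failure. The same log entry can then be scored in two ways on the primary endpoint, and 15.4.1 does not say which applies.

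Under the literal reading, forgetting tablets, which the plan measures separately, becomes part of the efficacy outcome. The example in 9.4.2 is the same drug and dose as the scheduled ondansetron in 10.7.3, so drug and dose alone cannot tell a late scheduled dose from rescue. The trial is unblinded (9.5, 9.6), so the scoring rule should be fixed in writing and not decided entry by entry.

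**Working it through.** **1. One patient scored under each definition.** Take a patient with no nausea and no vomiting in weeks 1-2 who replaces one forgotten ondansetron dose, documented as such.

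| Outcome | Score |
|---|---|
| CR, literal (9.4.2 with 15.4.1) | Failure |
| CR, rescue read as in 9.4.1 and 9.4.3 | Response |
| Nausea CR (15.5.2) | Response: no rescue for nausea |
| Vomiting CR (15.5.2) | Response: no rescue for vomiting |

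The literal reading thus fails a patient on the combined endpoint who responds on both of its separate counterparts.

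**2. The plan's power figures.** Inputs from 15.7.2: N = 57, one-sided 0.05, and 80% power for CR of 75% vs 97% or 63% vs 90%. Allocation is 1:1 (9.6).

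Pooled normal approximation with n = 28.5 per arm, mean rate p̄ and difference Δ:

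power = Φ{[Δ − 1.645·√(2p̄(1−p̄)/n)] / √([p₀(1−p₀)+p₁(1−p₁)]/n)}

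For 75% vs 97%: p̄ = 0.86, so power = Φ[(0.22 − 1.645 × 0.0919)/0.0872] = Φ(0.789) = 78.5%. For 63% vs 90% it is 78.8%.

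Exact enumeration of the one-sided uncorrected chi-square test with 28 ondansetron and 29 combination patients gives 83.9% and 81.7%. The stated 80% lies between the two methods and is reproduced.

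**3. Illustration of the literal reading.** The documents give no rate of replaced doses. Assume that a share q of would-be responders, the same in both arms, fails only because of a replacement dose. Each CR rate p becomes p(1−q), and the difference becomes Δ(1−q).

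Exact power, 28 ondansetron and 29 combination patients (reverse split in brackets):

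| q | 75% vs 97% | 63% vs 90% |
|---|---|---|
| 0 | 83.9% (85.5%) | 81.7% (80.3%) |
| 1% | 80.3% (81.6%) | 79.9% (78.6%) |
| 2% | 77.1% (77.9%) | 78.1% (77.0%) |
| 5% | 69.1% (68.2%) | 72.9% (72.0%) |

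In patients:

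- 75% vs 97%: expected responders are 28 × 0.75 + 29 × 0.97 = 49.1. The three non-zero values of q fail 0.49, 0.98 and 2.46 of them.
- 63% vs 90%: 28 × 0.63 + 29 × 0.90 = 43.7, giving 0.44, 0.87 and 2.19.

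The 22-point difference becomes 22.0 × (1−q) = 21.8, 21.6 or 20.9 points.

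**4. Direction.** Both arms take ondansetron daily, so most of the effect would be shared: both rates fall and the difference narrows. Exact equality is not assured. In the primary window the combination arm has one more dose to forget, rolapitant on day 1.

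**5. With rescue limited to symptoms,** the planning rates are unchanged and the power figures in step 2 stand.

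**The case against.** The strongest case is that 9.4.2 contains one loose word and the rest of the document already settles the meaning. Sections 5.3, 9.1, 9.4.1 and 12.2 speak of rescue as an additional antiemetic, and a dose that replaces a scheduled one is not additional. Sections 9.4.3, 15.5.2 and 15.7.1 point the same way. CR is scored from the modified MAT, and use is recorded in sequence-specific logs. These are attachments that are not shown, and they may already keep replacement doses apart. Weekly reminder calls may keep missed doses rare, and 15.4 already accepts that 57 patients may give too little power.

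Most of this stands, and it keeps the point small. What remains is that no passage resolves the scoring. Sections 9.4.1 and 9.4.3 give permission and logging instructions, not an endpoint definition. Section 15.7.1 explains a planning rate, uses non-exhaustive wording and does not amend 15.4.1. If the intent is clear, one sentence is enough to record it.

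A reader might infer that compliance problems will materially erode power. At an assumed q of 10%, for example, the normal approximation for 75% vs 97% gives 55.8%. The documents do not support this: 7.3 calls compliance a problem but gives no rate of missed doses, still less of doses that were replaced and were the only reason for failure.

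**Conclusion.** The point holds as a wording fault on the primary endpoint: followed as written, 9.4.2 and 15.4.1 together fail a symptom-free patient. Severity is minor. The symptom-linked reading is very probably the intended one, and the practical effect is unknown and possibly nil.

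The power figures rest on assumed values of q, equal effect in both arms and a 28/29 split. They show sensitivity at this sample size and do not estimate a loss. At 1-2% about one patient or fewer is affected.

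Two stronger readings should be avoided. The documents do not show that CR is in fact being scored the literal way, because the forms are not available. Nor do they show a bias for or against the combination: the extra rolapitant dose makes unequal effects possible, but no figure indicates that they occur.

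**What to change.** Reconcile 9.4.2 with 9.4.1, 9.4.3 and 15.4.1 on what counts as rescue. How a missed dose is handled clinically stays with the protocol authors.

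Before the primary analysis, state in 15.4.1 that:

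- for CR, rescue means an antiemetic taken to treat nausea or vomiting;
- a dose documented as replacing a missed scheduled dose counts toward compliance only;
- an entry with no documented reason stays as rescue.

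Add one sensitivity analysis that counts every replacement dose as rescue.

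Classification should rest on the documented reason, for which the weekly validation calls in Section 12 are a source. Clock times may be missing, because 9.4.3 provides only for dates of rescue use. Nausea reported nearby should not decide it either. Untreated nausea is not a CR failure, and MAT reports cover days 2-3 and 4-6 together, so 5 of 7 days each week (10 of 14 in the primary window) fall in a multi-day report.

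The cost is a rewording of 9.4.2, a short addition to 15.4.1, one derivation rule and one extra analysis. No new log field is needed; 53 of the 57 patients had been randomized by mid-January 2022. The downside is some judgement in classifying existing entries in an unblinded trial, contained by the default to rescue and by the sensitivity analysis.
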